29 JAN 2020

Page 37 of 102 Confidential

TEVA Pharmaceuticals USA, Inc.

Protocol No.: OXY2018-01 Version No.: 3.0;

- 1. Niacin <500 mg/day if not at a stable dose or if it is known to cause flushing.
- 2. Vitamins in quantities above the recommended daily dose (e.g., Vitamin A above about 10,000 IU).
- and minor injuries; Low dose aspirin is also allowed); Subjects will also be allowed to use acetaminophen for pain relief, as needed. The acceptable The use of anti-inflammatory medications (e.g., NSAIDs). NSAID use allowed on as needed basis for conditions such as headache, menstrual cramps, maximum dosage of acetaminophen should be 3,000mg/day.
- Subject has to refrain from changing the use of any concomitant therapies after the screening visit until study completion. 4.

Page 38 of 102 Confidential

Protocol No.: OXY2018-01 Version No.: 3.0; 29 JAN 2020

4.4 Subject Withdrawal / Dropout

Study subjects will be discontinued from the study for any of the following reasons:

- 1. If the study subject withdraws his or her consent for any reason.
- 2. Subjects who discontinue treatment early due to insufficient or lack of treatment effect or whose condition worsens and require alternate or supplemental therapy for the treatment of moderate to severe persistent facial erythema of rosacea, the subjects should be discontinued, but included in the PP population analysis as treatment failures and provided with effective treatment.
- 3. Subjects that withdraw or discontinue early for reasons other than lack of treatment effect should be excluded from the PP population, but included in the mITT population, using last observation carried forward (LOCF).
- 4. If the study subject's drug code is un-blinded.
- 5. If an AE occurs for which the study subject desires to discontinue treatment or the Investigator determines that it is in the study subject's best interest to be discontinued.
- 6. If the subject experiences an SAE.
- 7. If there is a protocol violation.
- 8. If a concomitant therapy is reported or required which is prohibited or may interfere with the results of the study.
- 9. If the study subject is lost to follow-up.
- 10. If the study subject becomes pregnant (refer to Section 6.5.4)

- 12. Administrative reasons.
- 13. Any other reason that may affect the outcome of the study or the safety of study subjects.
- *A protocol violation is defined as any study subject or Investigator activity that could have possibly interfered with the therapeutic administration of the treatment or the precise evaluation of treatment efficacy that affects the rights, well-being or safety of the subject or the scientific integrity of the study data.

If a subject discontinues participation in the study, every attempt will be made to complete the EoT as indicated in Table 6-1, and any outstanding data and study medication will be collected if possible. The reasons for a discontinuation and the date of removal from the study will be documented on the electronic Case Report Form (eCRF) and Sponsor will be notified.

Before a study subject is considered lost to follow-up, the Investigator will document all attempts to reach the study subject twice by telephone and will send a follow-up letter.

In the event of discontinuation of a subject from the study at any time due to an AE, the reason for discontinuation, the nature of the event and its clinical course must be fully documented. For such a study subject, the Investigator must strive to follow the study subject until the AE has resolved, become clinically insignificant, is stabilized or the study subject is

Confidential Page 39 of 102

Protocol No.: OXY2018-01 Version No.: 3.0; 29 JAN 2020

lost to follow-up. Should an SAE be noted, procedures stated in Section 6.5.1 must be followed.

When a study subject discontinues the study due to any of the above reasons, the study subjects should be prescribed appropriate treatment that he/she can continue to use as per the Investigator's clinical judgment.

Confidential Page 40 of 102

TEVA Pharmaceuticals USA, Inc.

Protocol No.: OXY2018-01 Version No.: 3.0; 29 JAN 2020

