12 PREMATURE TERMINATION OF STUDY/SUBJECT

A subject may terminate from the study early for any reason at any time without any disadvantages. In this case, the Investigator should make every effort to have the subject return to the next scheduled visit to perform all required Study Completion/Early Termination visit activities and to collect and reconcile all test articles. If the subject does not return for the Study Completion/Early Termination visit, the site should fully document the reason for early termination. All data, including the date and primary reason for termination, must be recorded on the Study Completion/Early Termination CRF, and source document.

Version No.: 3.0;

Any subject who experiences an AE may be terminated from the study or from study treatment at any time at the discretion of the Investigator. In this case, the subject should be followed at the discretion of the Investigator until the resolution or stabilization of the AE. All applicable data should be recorded in the AEs section of the CRF. If a subject terminates from the study early for multiple reasons that include AEs, the Study Completion/Early Termination CRF should indicate that early termination was related to an AE.

An exception to this requirement will be the occurrence of an AE that in the opinion of the Investigator is not severe enough to warrant early termination but that requires the use of a prohibited medication, thereby requiring discontinuation of the subject. In such a case, the reason for discontinuation would be the need to take a prohibited medication, not the AE.

The Investigator must inform the clinical project physician/clinical leader/Principal Investigator as soon as possible of all subjects who are being considered for early termination due to AEs. Additional reports must be provided when requested.

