6.2 Modified Intent to Treat Population (mITT Population)

The mITT population includes all randomized subjects who met all the inclusion and none of the exclusion criteria, have a CEA measurement at baseline (i.e. pre-dose on Day 1), applied at least one dose of study treatment, and have at least one post-baseline measurement for CEA or discontinue due to lack of treatment effect after completing 2 days of treatment.

This population will be used for analyses of superiority.

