6.3 Per Protocol Population (PP Population)

The PP population includes all subjects in the mITT population who have no major protocol deviations/violations that would affect the treatment evaluation.

See section 7.5 for more details on protocol deviations and how they affect exclusion from the PP population.

The PP population will be used for analyses of therapeutic equivalence.

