7.6.2 Derivation of the Primary Endpoint

A subject is defined as achieving treatment success at a time-point if the CEA score is at least 2 grades lower than the baseline value of the score. In this case baseline is defined as the predose assessment on Day 1. To achieve the primary endpoint, the subject needs to have treatment success at all 4 post-application timepoints (3, 6, 9 and 12 hours) on Day 29.

The CEA score at all post-application time-points on Day 29 as well as the pre-treatment
assessment on Day 1 are required to determine the primary endpoint.

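### Protocol 4.4 item 7 makes withdrawal mandatory for a protocol violation, so some Day 29 scores that could have been observed are replaced by carried-forward values, mainly in mITT

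*Protocol*

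**What the plan says.** The list in Protocol 4.4 opens with mandatory wording (subjects will, not may, be discontinued). Item 7 is "If there is a protocol violation". The footnote defines a violation as "any study subject or Investigator activity that could have possibly interfered with the therapeutic administration of the treatment or the precise evaluation" of efficacy, and adds that the activity must affect the subject's rights, welfare or safety, or the integrity of the data.

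Item 3 sets the consequence. Subjects who leave early for reasons other than lack of effect "should be excluded from the PP population, but included in the mITT population, using last observation carried forward (LOCF").

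The SAP decides PP membership separately. Section 6.3 keeps mITT subjects "who have no major protocol deviations/violations that would affect the treatment evaluation" and refers to Section 7.5 for detail. Section 6.2 limits mITT to "all randomized subjects who met all the inclusion and none of the exclusion criteria", with further conditions on dosing and on erythema (CEA) measurements. Under Section 7.6.2, to meet the primary endpoint "the subject needs to have treatment success at all 4 post-application timepoints (3, 6, 9 and 12 hours) on Day 29".

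**The concern.** Item 7 takes a decision that belongs to the analysis and makes it during conduct, where it cannot be undone. Elsewhere the plan expects subjects with lapses to continue. Protocol 5.7 has missed and extra applications entered on the compliance page, Protocol 6.7 has off-protocol dosing reported on the eCRF, and SAP 7.7.5 summarises compliance and missed doses. None of these calls for withdrawal. A site's own act can also trigger item 7 against a compliant subject.

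The endpoint is a Day 29 result. Once a subject is withdrawn earlier, the mITT comparison uses a carried score where a real one could have been collected. PP may also lose a subject whom SAP 6.3 would have kept.

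**Working it through.** Neither document shows a sample size, dropout allowance or violation rate, so there is no figure of the plan's own to reproduce. The wording is compared first. The arithmetic after that is illustration on assumed inputs.

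**1. The two rules side by side**

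| | Protocol 4.4 item 7 and footnote | SAP 6.3 |
|---|---|---|
| Applied | During conduct | At analysis |
| Threshold | Possible interference, plus an effect on rights, welfare, safety or data integrity | Major, and would affect the treatment evaluation |
| Result | Discontinued from the study | Out of PP only |

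The rules overlap but are not the same. For example, a violation that possibly interferes and bears only on rights can meet the first without meeting the second.

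**2. Who loses an observed Day 29 result**

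- Eligibility violators: no mITT loss, because SAP 6.2 excludes them already.
- Violation found after the Day 29 assessments: nothing is lost.
- Violation before Day 29 that SAP 6.3 would call major: PP is lost either way. The avoidable loss is the Day 29 result in mITT.
- Violation before Day 29 that is not major: both are lost.

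Scheduled post-dose CEA scores exist only on Day 1 and Day 29. The carried score therefore comes from Day 1, from an early discontinuation visit (Protocol 6.2), or from a return visit under Protocol 12.

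**3. mITT (superiority)**

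Assume a share s of 1 to 5% per arm is withdrawn under item 7 but could have stayed. Let d be the active-minus-vehicle difference and f the fraction of d that the carried scores lose, from 0 to 1. Then dilution = s × d × f.

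Values of d come from Table 2 of the prescribing information (Protocol Appendix II), at hours 3, 6, 9 and 12:

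- Trial 1: 12−6=6, 16−8=8, 18−6=12, 15−6=9 points.
- Trial 2: 14−7=7, 13−5=8, 16−9=7, 12−6=6 points.

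That endpoint combines clinician and subject scores at single time points, so it is only a guide. With f=0 the dilution is 0. With f=1 it runs from 0.01×6=0.06 to 0.05×12=0.60 points.

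For power, take 15% against 6% (Trial 1, hour 12), s=5%, and every carried value a failure. The rates become 0.95×15=14.25% and 0.95×6=5.70%, a difference of 8.55 points instead of 9.0. The formula is power = Φ{[d − 1.96√(2p̄(1−p̄)/n)] / √[(pA(1−pA)+pP(1−pP))/n]}, an unstratified approximation to the planned exact test.

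| Assumed n per arm | No withdrawals | 5% withdrawn, all carried as failures |
|---|---|---|
| 150 | 72.2% | 69.7% |
| 220 | 87.1% | 85.2% |
| 300 | 95.1% | 93.9% |

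**4. PP (equivalence)**

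The continuity-corrected 90% half-width at an observed difference of 0 is 1.6449·√(2p(1−p)/n) + 1/n, with n and p assumed.

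| n per arm | p | No loss | 1% loss | 5% loss |
|---|---|---|---|---|
| 100 | 0.15 | 0.0931 | 0.0936 (+0.56%) | 0.0957 (+2.88%) |
| 100 | 0.50 | 0.1263 | 0.1270 (+0.54%) | 0.1299 (+2.81%) |
| 300 | 0.15 | 0.0513 | +0.54% | 0.0527 (+2.77%) |
| 300 | 0.50 | 0.0705 | +0.53% | 0.0724 (+2.72%) |

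These rows treat every withdrawal as avoidable in PP. If half would leave PP anyway, the avoidable loss is 0.5 to 2.5% and the widening is 0.3 to 1.4%. It is nil if replacements are randomized, which the Synopsis permits.

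**The case against.** The footnote has two limbs. Possible interference is not enough alone: the activity must also affect rights, safety or data integrity. A reader might infer that any trivial deviation forces withdrawal. The text does not support that, because the second limb works as a materiality filter. This stands, and it narrows the group.

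SAP 7.5, which governs deviations, is not visible. It may define major deviations broadly enough to cover nearly every item 7 case. No contradiction with it can be claimed, and the PP part of the concern depends on it.

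Some data may be recovered. Protocol 4.4 asks for an attempt at the end-of-treatment procedures, Protocol 6.2 applies the Day 29 procedures at an early discontinuation visit, and Protocol 12 asks for a return at the next scheduled visit. The only site visit after Day 1 is Day 29, so a four-time-point profile may be obtained near Day 29, possibly off treatment. This softens the mITT loss. It does not help PP, because item 3 still excludes the subject. How carried values map to the four time points is not visible.

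The direction is mostly conservative. Wider intervals and diluted differences make both tests harder to pass, and no bias toward false equivalence or false superiority is shown.

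A reader might also infer that item 6, "If the subject experiences an SAE", conflicts with Protocol 12, under which a subject with an adverse event "may be terminated from the study or from study treatment at any time at the discretion of the Investigator". The documents do not establish that. Item 5 is the general adverse-event rule and fits Protocol 12. Item 6 is a specific, stricter rule for serious events, and the two can coexist. Relaxing it would be a safety trade-off for a drug whose label carries cardiovascular and vascular warnings, so no change to item 6 is proposed.

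**Conclusion.** The point holds in a narrow form. Items 7 and 3 together withdraw some subjects before Day 29 whose results could have been observed, although SAP 6.3 can settle PP membership at analysis. The avoidable loss falls mainly on Day 29 CEA data in mITT. Any PP loss is confined to violations that SAP 6.3 and 7.5 would not treat as major.

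The size is unknown and probably small. At an assumed 1 to 5% avoidable withdrawal, mITT dilution is 0 to 0.6 points. In the power illustration the loss is 1.2 to 2.5 percentage points, on the pessimistic assumption that every carried value is a failure. In PP, the widest half-width in the illustration rises from 0.126 to 0.130 against a margin of 0.20. This is a cheap improvement, not a threat to the trial's conclusions.

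**What to change.** Reword item 7 so that a violation is recorded and the subject stays on study through the Day 29 assessments, unless continuing is unsafe or consent or the subject's rights are compromised. Decide PP exclusion under SAP 6.3 and 7.5 before unblinding.

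Narrow item 13 at the same time. It now mandates withdrawal for any other reason that might affect the study's outcome, which would recapture the same cases. Limit it to safety or rights. Leave item 6 as it is.

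The cost is a protocol wording change and a few more 12-hour Day 29 visits.

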5 TREATMENTS

5.1 Treatments to be Administered

The IPs supplied by the Sponsor will consist of the following:

Test Product

Name of the product : Oxymetazoline hydrochloride Cream, 1%

Active ingredient(s) : Oxymetazoline hydrochloride

Pharmaceutical dosage form : Cream

Strength : 1% (each gram of cream contains 10 mg [1%]

oxymetazoline hydrochloride, equivalent to 8.8 mg

[0.88%] of oxymetazoline free base)

Route of administration : Topical

Manufacturer : Actavis Laboratories, Salt Lake City, UT (a subsidiary of

Teva Pharmaceuticals, USA)

Reference (R)

Name of the product : RHOFADETM (Oxymetazoline hydrochloride Cream,

1%)

Active ingredient(s) : Oxymetazoline hydrochloride

Pharmaceutical dosage form : Cream

Strength : 1% (each gram of cream contains 10 mg [1%]

oxymetazoline hydrochloride, equivalent to 8.8 mg

[0.88%] of oxymetazoline free base)

Route of administration : Topical

Manufacturer/Marketed by : Manufactured by DPT Laboratories Ltd, for Allergan

Placebo (Vehicle)

Name of the product : Vehicle to Oxymetazoline hydrochloride Cream

Active ingredient(s) : NA

Pharmaceutical dosage form : Cream

Strength : NA

Route of administration : Topical

Manufacturer : Actavis Laboratories, Salt Lake City, UT (a subsidiary of

Teva Pharmaceuticals, USA)

Confidential Page 41 of 102

Protocol No.: OXY2018-01

5.2 Treatment Assignment (Randomization)

The kit number will correspond to a computer-generated randomization schedule assigning that number to one of the three study treatment groups.

The study subject numbers will be assigned to study subjects sequentially in the order in which study subjects are enrolled into the study.

5.3 Dosage and Administration

The study medication will be dispensed to the subjects on Day 1 at the study site. Subjects will gently wash their face with a mild, non-medicated cleanser (a), rinse with warm water and pat dry. The subjects will be asked to apply a pea-size amount of the assigned study treatment cream to cover the entire face [forehead, chin, nose, and each cheek (avoiding the eyes and lips)], once daily, preferably at the same time each day, for 29 days. Subjects will be instructed to avoid applying the study medication to the eyes, eyelids, lips, mouth, scalp, neck, ears, and any membrane of the inner nose, or open wounds. Subjects will be required to wash their hands before and after each application of study treatment.

On Day 1 and Day 29, the dose will be applied in the morning after completion of pre-dose study assessments and procedures.

5.4 Receipt and Storage

Investigational Products (IPs) should be stored at 20°C-25°C (68°F-77°F), excursions permitted to 15°C-30°C (59°F-86°F) [see USP Controlled Room Temperature]; in a secured, authorized access area at the investigative site.

5.5 Packaging and Labeling

The randomization will be pre-planned according to a computer-generated randomization schedule. The study medication will be blinded, packaged and delivered to the site in bulk. The study medication will be labeled and packaged such that neither the study subject nor the Investigator can identify the treatment. The labeling and packaging scheme will be outlined in a separate document by the Sponsor. The study medications will be shipped to the Investigator's site from a centralized location. The Principal Investigator will be responsible for ensuring that all study products are stored in a locked, secure location, with access limited to the Investigator and his/her designee(s). An accurate inventory of the study medication will be maintained in accordance with federal regulations.

Confidential Page 42 of 102

5.6 Blinding

This is a double-blinded clinical end point bioequivalence study. Study medications will be provided in similar cartons to maintain study blinding.

If necessary, for the safety and proper treatment of the subjects, the Investigator can unblind the subject's treatment assignment to conduct appropriate follow-up care. Whenever possible, the Sponsor or medical monitor will be notified before unblinding the study medication. The date and signature of the person breaking the code as well as the reason for breaking the code and any associated AEs will be recorded in the subject's source documentation.

The Investigator, staff at the study site, study monitors, and data analysis/management personnel will be blinded to the treatment assigned to the subject. The study site will have at least one Independent Dispenser. The role of the unblinded Independent Dispenser will be to dispense and collect study medication to/from the subjects, maintain dispensing records, and ensure the study medication logs are complete and accurate. The Independent Dispenser will also be responsible for observing and supervising the administration of the study medication by the subject on clinic visits, Day 1 and Day 29. The subject will be requested not to discuss the appearance of the study medication with the Investigator or study staff outside of the Independent Dispenser. Independent dispenser should not participate in any activities other than the activities defined in this section. To ensure that information that could potentially bias handling of data is not disclosed, the packaging team will hold the randomization scheme until after database lock.

At the conclusion of the study, after the database has been locked, each site will be sent the study randomization scheme (respective to their site) that should be retained with the study documents in the event of an FDA inspection along with evidence of when the randomization scheme was provided.

Confidential Page 43 of 102

5.7 Assessment of Compliance

A subject diary will be provided to all subjects on Day 1 where it is required to document the date and time of application of the study medication. In the subject diary, subjects will also note any AE observed and any concomitant medication taken or changes.

Compliance will be determined from the subject diary, which the subject will be trained and instructed to use to record the application of study medication each day, as well as all missed applications. The number of missed and additional applications will be captured on the compliance page of the CRF.

5.8 Study Medication Replacement

In the event of loss/spillage, extra tubes of study medication may need to be dispensed. See IMP manual for details.

Before dispensing the replacement study medication, the information will be recorded on the Study Medication Accountability Log.

5.9 Accountability of Study Medication

It is the responsibility of the Investigator to ensure that the accountability of the IP is maintained at the study site where study medication is stored and dispensed.

A Drug Accountability Log will assist study site staff in maintaining inventory records of study medication.

The study medications will be dispensed only by an appropriately Independent dispenser. Study subjects must return used/unused IP to the Independent Dispenser. Any remaining drug supplies can be accounted for and noted in the Drug Accountability Log. The original Drug Accountability Log must remain at the study site and a copy should be provided to the study monitor after the study. See IMP manual for details.

5.10 Retention of Study Medication Samples

Retention samples should be randomly selected from the drug supplies received prior to dispensing to subjects.

Confidential Page 44 of 102

Protocol No.: OXY2018-01 Version No.: 3.0; 29 JAN 2020

5.11 Return of Drug Supplies

With the exception of the retention samples, all remaining IP will be returned by the Investigator or designee to the designated drug depot for storage and / or destruction after the close-out visit,

Confidential Page 45 of 102

Protocol No.: OXY2018-01

6 STUDY PROCEDURES

6.1 Schedule of Events

The study will include the following scheduled visits: Screening visit

Baseline visit (Day 1), Telephone Follow-up visit (Day 14) and EoT visit (Day 29).

The schedule of visits and the study assessments at each visit are presented in Table 6-1. The assessments will be performed by, or under the supervision of, an Investigator or a qualified delegate. Evaluations should be performed by the same evaluator throughout the study whenever possible. Additional examinations may be performed as necessary to ensure the safety and well-being of subjects during the study.

Signs and symptoms that existed before signing informed consent should be recorded as medical history findings. Signs and symptoms that worsen after the informed consent is signed as well as any sign or symptom that begins after the ICF is signed (even if before start of study treatment) should be recorded on an AE page of the eCRF using Common Terminology Criteria for Adverse Events (CTCAE), version 4.03 (see Section 6.5.1).

Confidential Page 46 of 102

Version No.: 3.0;

TEVA Pharmaceuticals USA, Inc. Protocol No.: OXY2018-01

Table 6-1: Schedule of Events				200	
Procedures	Screening A	Screening B	Day 1 (Baseline)	VISIT Day 14 (Telephone Follow-up) ^a	Day 29 (EoT)
Written informed consent	×				
Demographics (height, weight, body mass index (BMI), gender, race, ethnicity)	×				
Pregnancy test (Urine)	×	×	×		×
Medical and surgical history	××	×			
Prior and concomitant medications and concurrent procedures	×	×	×	×	×
Vital signs measurements (blood pressure, heart rate, body temperature)	×	×	Pre-dose and 12 hrs		Pre-dose and 12 hrs
Clinician Erythema Assessment (CEA)	X	×	Pre-dose, 3, 6, 9, and		Pre-dose, 3, 6, 9, and
Confidential		Page	Page 47 of 102		

TEVA Pharmaceuticals USA, Inc. Protocol No.: OXY2018-01

Version No.: 3.0;

